13.2 ANALYSIS OF LABORATORY PARAMETERS

Not applicable for this study.

13.3 ELECTROCARDIOGRAM

Cardiac rhythm will be evaluated as described in Sections 8.2 and 8.3. Abnormal ECG findings will be recorded as SAE.

13.4 Physical examination parameters

Subject Clinical Assessment will be evaluated as described in Section 8.3.

14 SUBGROUP ANALYSIS

Subject disposition will be described within each subgroup population as detailed in the corresponding paragraph in Section 7.1.

Primary analyses will be summarized by specific subgroups (subject symptoms, ACT/DATP, Core Lab evaluation) as described in Section 5.3. A forest plot will be used to graphically represent

COPYRIGHT LIVANOVA. ALL RIGHTS RESERVED. MAY NOT BE REPRODUCED WITHOUT PERMISSION. ALL HARD COPIES SHOULD BE CHECKED AGAINST THE CURRENT ELECTRONIC VERSION WITHIN MASTERCONTROL PRIOR TO USE AND DESTROYED PROMPTLY THEREAFTER. ALL HARD COPIES ARE CONSIDERED UNCONTROLLED DOCUMENTS.

LN-GLB-CLN-TEM-0033 rev1 Page 29 of 42

the estimate point of the proportion together with its 90% CI in each subgroup; number of subjects with reduced leaflet motion and number of total subject in each subgroup will be also displayed.

Tabular presentations for all secondary endpoints will be done by group defined in Section 5.3 as described in the corresponding paragraph:

- "Secondary Efficacy Analysis" (Section 11)
- "Secondary Performance Analysis" (Section 12)

Specific analysis will be performed within symptomatic/asymptomatic grouping as described in Section 11.2 "Incidence of reduced leaflet motion in symptomatic and asymptomatic subjects".

15 INTERIM ANALYSIS

Not applicable for this study.

16 ABBREVIATIONS

Acronym	Verbatim
4D	Four Dimensional
ACT	Anticoagulant (therapy)
AdaM	Analysis Data Model
ANOVA	Analysis of Variance
вмі	Body Mass Index
BSA	Body Surface Area
CI	Confidence Interval
CIP	Clinical Investigational Plan
CSR	Clinical Study Report
ст	Computed Tomography (scan)
DAPT	Dual Antiplatelet Therapy
DBP	Diastolic Blood Pressure
ECG	Electrocardiogram
EF	Ejection Fraction
EOA	Effective Orifice Area
FDA	Food and Drug Administration
HR	Hazard Ratio
IVSd	Interventricular Septal Thicknesses-Diastole
IFU	Instruction For Use

COPYRIGHT LIVANOVA. ALL RIGHTS RESERVED. MAY NOT BE REPRODUCED WITHOUT PERMISSION. ALL HARD COPIES SHOULD BE CHECKED AGAINST THE CURRENT ELECTRONIC VERSION WITHIN MASTERCONTROL PRIOR TO USE AND DESTROYED PROMPTLY THEREAFTER. ALL HARD COPIES ARE CONSIDERED UNCONTROLLED DOCUMENTS.

LN-GLB-CLN-TEM-0033 rev1 Page 30 of 42

Ιπ	Intention-To-Treat population
LVEDV	Left Ventricular End-Diastolic Volume
LVESV	Left Ventricular End-Systolic Volume
LVIDd	Left Ventricular Internal Dimension-Diastole
LVIDs	Left Ventricular Internal Dimension-Systole
LVOT	Left Ventricular Outflow Tract
LVEF	Left Ventricular Ejection Fraction
МІ	Multiple Imputation
MPG	Mean Pressure Gradient
NYHA	New York Heart Association
PER	Primary Endpoint-Related (major protocol deviation)
Pl	Principal Investigator
PP	Per-Protocol population
PPG	Peak Pressure Gradient
PTCA	Previous Carotid Artery Intervention or Percutaneous Transluminal Carotid Angioplasty
PWd	Posterior Wall Diameter
QC	Quality Control
RVSP	Right ventricular systolic pressure
SAE	Serious Adverse Event
SAF	Safety population
SAP	Statistical Analysis Plan
SBP	Systolic Blood Pressure
SCR	Screening population
TESAE	Treatment Emergent Serious Adverse Event
TEE	Transesophageal Echocardiogram
TIA	Transient Ischemic Attack
TTE	Transthoracic Echocardiogram

18 APPENDIX 1: ANALYSIS SPECIFICATIONS

The purpose of this section is to give technical details for the implementation of the SAP.

Study: APR002 BELIEVE

18.1 Percentages and decimal places

If not otherwise specified, the following rules are applied:

- Percentages are presented to 1 decimal point.
- Percentages equal to 0 or 100 are presented as such without a decimal point.
- For descriptive summary statistics, the same number of decimal places as in the raw data are presented when reporting minimum and maximum values, 1 more decimal place when reporting mean, median, quartiles and confidence interval (CI) and standard deviation (SD).
- P-values are presented to 3 decimal points. P-values < 0.001 will be reported as such.
- Ratios are presented to 3 decimal points.

The above described displaying rules must not be changed (e.g., rounding) for the CSR text and are used 1:1 in the body report as well.

18.2 Presentation of differences and changes

For changes from baseline, the later value will constitute the minuend and the baseline value the subtrahend. Changes will be calculated only for subjects with values at both considered visits.

18.3 Presentation of units

If applicable, parameters will be displayed together with the used unit of measurement. The unit of measurement is enclosed in square brackets ([]). This applies to both tables and listings.

18.4 Presentation of dates

Where applicable (e.g., in listings), dates will be displayed in ISO8601 format (example: 2014-09-29T12:16, see CDISC 2013). In case of incomplete dates, both the original value and the imputed value are displayed.

18.5 HANDLING OF MISSING VALUES

At each time point/visit, all subjects still in the study are reported. Missing values will be taken into account as missing in the analysis. The number of observed values and the number of missing values must sum up to the number of subjects in the study at the respective time point/visit.

Missing measurements/missing values are identified by the SDTM variable **STAT=ND. If this variable is not recorded (it's a permissible variable) the missing values of **ORRES should be used.

Unless otherwise specified in the SAP, missing values will not be imputed. If missing values are imputed, the result of all imputation strategies and newly derived information must be stored

COPYRIGHT LIVANOVA. ALL RIGHTS RESERVED. MAY NOT BE REPRODUCED WITHOUT PERMISSION. ALL HARD COPIES SHOULD BE CHECKED AGAINST THE CURRENT ELECTRONIC VERSION WITHIN MASTERCONTROL PRIOR TO USE AND DESTROYED PROMPTLY THEREAFTER. ALL HARD COPIES ARE CONSIDERED UNCONTROLLED DOCUMENTS.

in the ADaM data set. The shifts required for the shift tables should already be included in the ADaM data set.

Study: APR002 BELIEVE

Imputed values will be listed in the subject data listing and be marked as imputed.

18.6 VISIT WINDOWS

Measurements will be assigned to visits according to the windows allowed in the Protocol and reported in Figure 2. These are defined in Section 5.4 and resumed below:

- Pre-implant/implant: during and after successful implant.
- Hospital Discharge: ≤30 days post-implant.
- ACT/DAPT discontinuation visit: 1-6 months post-implant.
- First CT scan visit: ≥30 days (+ 60 days) after discharge (for subjects discharged off ACT/DAPT) or after ACT/DAPT discontinuation (for subjects discharged on ACT/DAPT).
- Second CT scan visit: after the first CT Scan and 6-10 months post-implant.
- 1 year visit: 1 year ± 1 month post-implant.

Figure 2: Visit Window Guide

Visit Name	Calculate from:	Window Start Day	Window Stop Day
Pre-Implant / Implant Data	Enrollment date	- 90	0
Hospital Discharge (completed prior to actual discharge)	Implant date	0	30
ACT / DAPT Discontinuation or Planning Visit	Implant date 90 days after Implant date preferred	30	180
1st CT-scan Follow-up Visit (no ACT/DAPT)	Hospital Discharge date 30 days after Hospital Discharge preferred	30	90
1st CT-scan Follow-up Visit (DC on ACT/DAPT)	ACT / DAPT Discontinuation date	60	240
2 nd CT-scan (if needed) A minimum of 6 weeks after 1 st CT-scan	Implant date	180	300
1 year follow-up	Implant date	335	395

18.7 CONVERSION OF TIME INTERVALS

If a time interval was calculated in minutes, hours or days and needs to be converted into months or years the following conversion factors will be used:

- 1 month = 30.4375 days
- 1 year = 365.25 days

18.8 MANDATORY TABLES WITHOUT DATA

Recommended tables must be created. If no subject qualifies for the table, the header will be created and the table itself will be replaced by "No subject in this category".

COPYRIGHT LIVANOVA. ALL RIGHTS RESERVED. MAY NOT BE REPRODUCED WITHOUT PERMISSION. ALL HARD COPIES SHOULD BE CHECKED AGAINST THE CURRENT ELECTRONIC VERSION WITHIN MASTERCONTROL PRIOR TO USE AND DESTROYED PROMPTLY THEREAFTER. ALL HARD COPIES ARE CONSIDERED UNCONTROLLED DOCUMENTS.

LN-GLB-CLN-TEM-0033 rev1 Page 34 of 42

18.9 STORING OF IMPUTATION DATA

The result of all imputation strategies (e.g., incomplete start dates of SAE), combination of observations (e.g., combination of consecutive SAEs) and new derived information (e.g., treatment-emergent flag) must be stored in ADaM data set.

18.10 OUTLIERS

Not applicable for this study.

18.11 HANDLING OF MISSING DATES FOR ADVERSE EVENTS

The term missing date refers to a completely missing date or to an incomplete date where parts are not available e.g., missing day.

[figure not shown]
Missing start and end date will be imputed conservatively, i.e., missing values will be imputed in such a way that the duration of the SAE is considered with the longest possible duration.

In case the SAE requires hospitalization, the hospitalization information could be added to the algorithm.

Figure 3: Graphical overview about the imputation strategy

LN-GLB-CLN-TEM-0033 rev1 Page 35 of 42

Study: APR002 BELIEVE

I1-I4: imputation steps C1-C4: checkpoints

Further explanations on the flow chart:

The different steps of the displayed imputation strategy must be completed from the first to the last step. All procedures in each step must be completed in the order given.

Imputation:

COPYRIGHT LIVANOVA. ALL RIGHTS RESERVED. MAY NOT BE REPRODUCED WITHOUT PERMISSION. ALL HARD COPIES SHOULD BE CHECKED AGAINST THE CURRENT ELECTRONIC VERSION WITHIN MASTERCONTROL PRIOR TO USE AND DESTROYED PROMPTLY THEREAFTER. ALL HARD COPIES ARE CONSIDERED UNCONTROLLED DOCUMENTS.

LN-GLB-CLN-TEM-0033 rev1 Page 36 of 42

• I1: Impute with date of first IMP - investigational medicinal product - (namely device implant).

Study: APR002 BELIEVE

• I2: Impute with first calendar day and / or first calendar month.

Imputation will be done based on the available partial information starting with month and then day. The respective first month and day will be chosen for imputation:

Missing date	Imputed date
■ 2014-Mar	2014-Mar -01
■ 2014	2014- Jan-01

- 13: Impute with date of informed consent signed.
- I4: Impute with last calendar day and / or calendar last month.
 Imputation will be done based on the available partial information starting with month and then day. The respective last month and day will be chosen for imputation:

Missing date	Imputed data
■ 2014-Mar	2014-Mar- 31
■ 2014	2014-Dec-31

Checkpoints:

- C1: The decision must be taken based on the available information (date) before imputation.
- C2: SAE stop date before first IMP
 - 1) The decision must be taken based on the available information (date) before imputation.
 - 2) If the end date is completely missing (with or without the information that the DAE was continuing) this will be considered as after first IMP.
 - 3) If no IMP was given this will be treated as SAE stop date before first IMP.
- C3: The decision must to be taken based on the available information (date) before imputation.
- C4: The decision must to be taken based on the available information (date) before imputation. A
 replacement of missing year for SAE start information is not foreseen. If needed, this will be
 considered on a case-by-case decision which must be documented together with the
 documentation of ADaM data sets.

Assignment SAEs to study periods

Assignment of SAE to study periods will be done after replacement of missing date information.

List of deaths

Death will be identified by outcome of SAE equals "fatal" (AETERM in "Sudden cardiac death", "Death unknown cause", "Death non cardiovascular") or SAE Criteria Met equals "death" or Reason for Termination equals "death".

Study: APR002 BELIEVE

Time to onset of SAE

Time to onset of SAE will be calculated based on implant date and based on the imputed value for SAE start date.

Duration of SAE

Duration of SAE will be calculated based on the imputed values for SAE start date and stop date. If duration of SAE could not be calculated due to unknown date information the following assessment to categories will be used:

- If the SAE is marked as "continuing" in the e-CRF the duration will be categorized as "continuing"
- Otherwise the duration category will be set to "missing".

18.12 TITLES AND FOOTNOTES

- Header: Company name, Study name and deliverable (e.g. LivaNova, Study APR002 BELIEVE
 Deliverables: Main Analysis)
- Footer: Cutoff date (if applicable), Snapshot date, Draft / Final
- Footnotes:
 - All the footnotes will begin with a dash followed by Trailing space, with indentation for second line when needed
 - Footnotes referring to a particular element of the Table, Listing or Figure, will have a standard order based on symbols as per American Medical Association (AMA) Manual of Style 10th Edition
 - Name and Version of the Coding System used, when coded events are reported
 - Final footnote will contain full program path and program name, Run/Execution date
- Title:
 - Title1: Table xx.x.x.x - Title 2: Table Title
 - Title 3: Analysis Population

Subgroup to be displayed as subtitle (preferably left aligned).

18.13 DATA DERIVATIONS

Derived variable	Derivation algorithm based on e-CRF version 8 dated 18 th July 2017
Concomitant	"Implant Surgical Details" e-CRF:
Procedures	Group "Implanted with a concomitant procedure" if CPYN= "Yes"
	Group "Implanted without a concomitant procedure" if CPYN= "No"
Subject symptoms	"Subject Clinical Assessment" e-CRF at "at 1 Month After ACT Dx (1st CT-Scan)" or "Reduced Leaflet Visit (2nd CT-Scan)" Visits:
	Group "Asymptomatic" if SCSYMPYN = "No"
	Group "Symptomatic" if SCSYMPYN = "Yes"
ACT/DATP	"Subject Clinical Assessment" and e-CRF:
	 Group "Subject on ACT/DAPT at hospital discharged (or 30-days after implant)" if SCDISCYN= "Yes"
	Group "Subject off ACT/DAPT at hospital discharged (or 30-days after implant" if SCDISCYN= "No"
Core Lab evaluation	"Vist (at 1 Month After ACT Dx or at Reduced Leaflet)" e-CRF:
by	Group "CT scan" if IMGTYPE= "4D CT Acquisition"
	Group "TEE" if IMGTYPE = "Transesophageal Echo"
Pre-implant period	If Enrolled Date= DXSTDAT2 ("Implant Surgical Details" e-CRF) then
	Start date: ICFDAT ("Inclusion/Exclusion Criteria" e-CRF)
	End date: DXSTDAT2 -1
	If Enrolled Date= ICFDAT then
	Start date=End date= "None".

LN-GLB-CLN-TEM-0033 rev1 Page 39 of 42

Post-implant period	If DXPER= "Yes" ("Implant Surgical Details" e-CRF) Start date: DXSTDAT2, End date: if SCDISCYN= "No" ("Subject Clinical Assessment" e-CRF) then End date= VISDAT (at Hospital Discharge visit) + 30 if SCDISCYN= "Yes" ("Subject Clinical Assessment" e-CRF) then End date= VISDAT (et ACT Disceptionation visit) + 30
Post-ACT/DAPT period	 End date= VISDAT (at ACT Discontinuation visit) + 30 Start date: if SCDISCYN= "No" ("Subject Clinical Assessment" e-CRF) then Start date= VISDAT (at Hospital Discharge visit) + 31 if SCDISCYN= "Yes" ("Subject Clinical Assessment" e-CRF) then Start date= VISDAT (at ACT Discontinuation visit) + 31 End date: VISDAT (at Year 1 visit)
Implant procedure completer	 DXPERF= "Yes" ("Implant Surgical Details" e-CRF) and DSSTDAT ≥ ACTDIDAT ("Study Termination" e-CRF) + 31 o if DSSTDAT missing, last available VISDAT ≥ ACTDIDAT + 31
Study completer	DSDECOD= "Completed" ("Study Termination" e-CRF)
SCR population	ICFDAT not missing ("Inclusion/Exclusion Criteria" e-CRF)
Enrolled Date	Derived from maximum between Consent Date and Implant Date. "Inclusion/Exclusion Criteria" e-CRF and "Implant Surgical Details" e-CRF Max(ICFDAT; DXSTDAT2)
ENR population	 SCR flag= "Yes" and DXSTDAT2 not missing ("Implant Surgical Details" e-CRF) and existing Enrolled Date
SAF population	 ENR flag= "Yes", and DXPERF= "Yes" ("Implant Surgical Details" e-CRF)
PP population	As reported in the Believe Risk Based Study Management Plan.
Time to study	"Implant Surgical Details" e-CRF and "Study Termination" e-CRF
termination (months)	[DSSTDAT – DXSTDAT2 + 1] / 30.4375

COPYRIGHT LIVANOVA. ALL RIGHTS RESERVED. MAY NOT BE REPRODUCED WITHOUT PERMISSION. ALL HARD COPIES SHOULD BE CHECKED AGAINST THE CURRENT ELECTRONIC VERSION WITHIN MASTERCONTROL PRIOR TO USE AND DESTROYED PROMPTLY THEREAFTER. ALL HARD COPIES ARE CONSIDERED UNCONTROLLED DOCUMENTS.

LN-GLB-CLN-TEM-0033 rev1 Page 40 of 42

Time to event	"Implant Surgical Details" e-CRF
(months)	[Even date – DXSTDAT2 + 1] / 30.4375 Subjects ongoing and who are free from event at the analysis cutoff date will be censored at the analysis cut-off date. Subjects who have discontinued without an event will be censored at the date of discontinuation.
Age at Enrollment (years)	"Demographics" e-CRF and "Inclusion/Exclusion Criteria" e-CRF Age= [ICFDAT - BRTHDAT + 1]/365.25 As only month and year of birth are reported in the CRF, 1 st day of the month will be used for birth date.
Change from baseline	Test Value at Visit X - Baseline Value

Where

ACTDIDAT = "Date Subject Discontinued ACT/DAPT Therapy"

BRTHDAT= "Date of Birth"

CPAETERM= "Complications/Please specify if any of the following intraoperative complications occurred. /AE Term"

CPYN= "Was concomitant procedure performed?"

DIMODEL= "Valve Model"

DSDECOD= "Reason for Termination"

DSSTDAT= "Date of Study Termination"

DVDECOD= "Deviation Description"

DVICSPEC= "If Informed Consent, specify reason"

DXPERF= "Was the implant successful?"

DXSTDAT2 = "Date of Implant"

ICFDAT = "Informed Consent Date"

IEYN= "Met All Eligibility Criteria?"

COPYRIGHT LIVANOVA. ALL RIGHTS RESERVED. MAY NOT BE REPRODUCED WITHOUT PERMISSION. ALL HARD COPIES SHOULD BE CHECKED AGAINST THE CURRENT ELECTRONIC VERSION WITHIN MASTERCONTROL PRIOR TO USE AND DESTROYED PROMPTLY THEREAFTER. ALL HARD COPIES ARE CONSIDERED UNCONTROLLED DOCUMENTS.

LN-GLB-CLN-TEM-0033 rev1 Page 41 of 42

IMGTYPE= "Specify the imaging modality currently being used for the subject"

MHCVDAT = "If Myocardial Infarction, date"

MHSTDAT3= "If Stroke, date"

NY= "No/Yes"

SCDISCYN= "Was the subject discharged on anticoagulant and/or dual platelet therapy?"

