7.5. ANTICOAGULATION / DUAL ANTIPLATELET DISCONTINUATION (OR PLANNING) VISIT

This visit may be done by the subject's primary care physician as part of the standard of care for the subject. If done at a location other than the research location, the documentation of the visit will need to be obtained, reviewed by the site PI, and filed in the subject's research records. The visit details may then be entered in the EDC

system and made available for monitoring/source data review. Any part of the evaluation not completed will be considered a protocol deviation.

For subjects discharged with anticoagulation or dual antiplatelet therapy, (see Appendix 4 for American College of Cardiology guidelines for anticoagulation therapy¹¹) an additional visit shall be performed to assess the possibility to stop the anticoagulation or antiplatelet therapy and plan the CT scan. The discontinuation of anticoagulation or antiplatelet therapy is usually around 3 months after surgery in subjects without a further clinical need for this treatment. This additional visit shall evaluate the following information:

- Subject status
- Physical evaluation (including cardiac rhythm and NYHA functional classification)
- Medications
- SAEs

Subjects which are not able to come off ACT/DAPT treatment will remain in the study and followed through the 1-year evaluation.

7.6. 1ST CT SCAN VISIT (1 TO 6 MONTHS FOLLOW-UP VISIT)

This visit is intended to be done a minimum of 30-days after the initial discontinuation of anti-coagulation or dual antiplatelet therapy; usually between 1-6 months postimplant, or at least one month after discharge for subjects discharged without anti-coagulation therapy. Follow-up evaluations are to be conducted in an office, hospital or clinic setting and are to be performed by the PI or his/her designee.

The following data listed below shall be collected:

- Subject status
- Physical evaluation (including cardiac rhythm and NYHA functional classification)
- Medications
- Hemodynamic data from TTE examination measured at investigational site (MPG; PPG, EOA, aortic regurgitation with severity and location)
- CT Scan

- TEE only in subjects that are unable to undergo CT scan at the time of followup
- Medications
- SAEs

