5.1 GENERAL PRINCIPLES

The statistical analysis will be performed on the analysis study database with SAS version 9.4 or above (SAS Institute, Cary, N.C.).

If two or more of the analysis sets as defined in Section 6 coincide or the difference is less than 5%, presentations will only be prepared for the population less restrictive.

The default significant level will be 10%. Confidence Intervals (CIs) will be calculated at 90% confidence level and all tests will be two-sided, unless otherwise specified in the description of the analyses.

All the data collected and derived in the study will be presented in subject data listings.

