5.4 DEFINITIONS

Investigational Device (ID)	PERCEVAL (PMA P150011)
Baseline	Last non-missing observation (scheduled or unscheduled) before implant.
	Measurements collected the day of implant, in absence of other time information, are considered baseline data.
	If a subject is missing the planned baseline collection, the previous non-missing evaluation will become the baseline value.
	If any observation will be available before or on the day of implant, an unscheduled assessment done before the discharged visit can be used as baseline.
Study Day Count	The day of implant is defined as study Day 1.
	Calculate the study day according to the following rules:
	If date < study Day 1 then study day = Date – study Day 1
	If date ≥ study Day 1 then study day = Date – study Day 1 +1

LN-GLB-CLN-TEM-0033 rev1 Page 10 of 42

Study phases	
Pre-implant (Screening)	Screening and pre-implant assessments, where informed consent is signed and eligible criteria are met, before subjects will be considered enrolled in the study.
Implant (Enrollment)	During the implant until the establishment of a successful procedure.
Hospital Discharge	Before the subject is discharged or within 30 days of implant.
ACT/DAPT discontinua- tion visit	Visit required only for subjects on ACT/DAPT at hospital discharge: from 1 to 6 months (3 months preferred) postimplant.
Follow-up evaluations: First CT scan	Minimum of 30 days (+ 60 days) after discharge or discontinuation of ACT/DAPT (expected from 1 to 6 months post-implant).
Second CT scan	For subject with reduced leaflet motion previously detected by Core Lab; after the 1^{st} CT scan, but prior to 1 year follow-up visit (expected from 6 to 10 months post-implant).
1 year	Clinic visit at 1 year ± 1 month after the day of the implant.
Pre-implant period	Period from signing of the informed consent until the day before the implant.
Post-implant period	Period from successful implantation of Perceval bioprosthetic heart valve to 30-days after hospital discharge visit (for subjects discharged off ACT/DAPT) or ACT/DAPT discontinuation visit (for subjects discharged on ACT/DAPT).
Post-ACT/DAPT period	Period from 31 st day after the hospital discharge (for subjects discharged off ACT/DAPT) or 1 st day after the ACT/DAPT discontinuation (for subjects discharged on ACT/DAPT) to 1 year visit.

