Pooling of sites and countries	Unless otherwise specified, data from all of the study sites and countries will be pooled and the analysis performed on the complete database including subjects from all sites and countries.
Screening Failure	Subjects who are screened, informed consent was obtained, and not included in the study due to eligible criteria not met.
Implant procedure completers	Subjects successfully implanted who complete the post-implant period, namely who discontinued the ACT/DAPT at minimum 30 days.

COPYRIGHT LIVANOVA. ALL RIGHTS RESERVED. MAY NOT BE REPRODUCED WITHOUT PERMISSION. ALL HARD COPIES SHOULD BE CHECKED AGAINST THE CURRENT ELECTRONIC VERSION WITHIN MASTERCONTROL PRIOR TO USE AND DESTROYED PROMPTLY THEREAFTER. ALL HARD COPIES ARE CONSIDERED UNCONTROLLED DOCUMENTS.

LN-GLB-CLN-TEM-0033 rev1 Page 11 of 42

Study completers

Subjects who complete the 1 year visit.

Study: APR002 BELIEVE

6 Analysis population

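### The SAP's implant procedure completer flag has no branch for subjects without an ACT/DAPT stop date, so no single handling of a blank date classifies both groups who lack one correctly

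*SAP*

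**What the plan says.** SAP 5.4 defines implant procedure completers as "Subjects successfully implanted who complete the post-implant period, namely who discontinued the ACT/DAPT at minimum 30 days". The post-implant period in the same section has two ends, depending on therapy at discharge. It runs from implant "to 30-days after hospital discharge visit (for subjects discharged off ACT/DAPT"), and to the discontinuation visit for those discharged on therapy.

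SAP 18.13 turns this into code. The post-implant and post-ACT/DAPT period rows both branch on SCDISCYN (discharged on therapy, yes or no). The completer row does not. It requires a successful implant and "DSSTDAT ≥ ACTDIDAT ('Study Termination' e-CRF) + 31", with the fallback "if DSSTDAT missing, last available VISDAT ≥ ACTDIDAT + 31". ACTDIDAT is labelled as the date on which the subject stopped ACT/DAPT. SAP 18.5 leaves missing values unimputed unless the SAP specifies otherwise, and it specifies nothing for this date.

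Both groups that would lack a stop date are foreseen. Protocol 6.3.6 times the CT from hospital discharge for subjects not on therapy at discharge, and SAP 5.4 requires the discontinuation visit only for subjects discharged on therapy. For those who cannot stop, Protocol 7.5 states: "Subjects which are not able to come off ACT/DAPT treatment will remain in the study and followed through the 1-year evaluation".

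SAP 7.1 reports the completer count in the disposition table, overall and for the SAP 5.3 subgroups, as a percentage of the safety population (SAF).

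**The concern.** The completer row tests every subject against a date that some subjects do not have. Its only fallback handles a missing termination date, not a missing stop date. The two groups without a stop date need opposite classifications: those discharged off therapy can complete the post-implant period, and those who never stop cannot. One convention for a blank date cannot serve both.

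At stake is a descriptive count with some interpretive weight. The primary objective concerns subjects off therapy for at least 30 days, while the primary analysis uses the SAF. This is the one row listed in SAP 7.1 that tells a reader how many subjects reached the off-therapy state. The on/off ACT/DAPT columns of that table are where an error would concentrate.

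**Working it through.** The plan states no figure for this row, so there is none to reproduce. The check applies the rule to subject profiles and then sizes the error over a range.

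**Inputs.** The rule, the field meanings and the period definitions come from SAP 5.4 and 18.13, and the target of about 88 subjects from SAP 2.3. Assumed: ACTDIDAT is blank for subjects discharged off therapy and for those who never stop. This is inferred from the field label and from the discontinuation visit applying only to on-therapy subjects; the e-CRF is not supplied. The days below are illustrative, with discharge on day 8.

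**Intended classification.** Discharged off: end date ≥ discharge + 31, i.e. ≥ 8 + 31 = day 39. Discharged on: a stop date exists and end date ≥ stop date + 31; for a stop on day 90, ≥ day 121.

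**Two conventions for a blank stop date.** (A) The comparison counts as not met. (B) It counts as met. SAP 5.1 says "The statistical analysis will be performed on the analysis study database with SAS version 9.4 or above". In SAS a missing value sorts below any date and missing + 31 stays missing, so a literal transcription gives B. That is knowledge of the software, not document text.

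| Profile | Intended | A | B |
|---|---|---|---|
| Off at discharge, followed to day 365 | completer | **no** | completer |
| Off at discharge, exits day 20 | no | no | **completer** |
| On, stops day 90, followed to day 365 | completer | completer | completer |
| On, stops day 90, exits day 100 | no | no | no |
| On, never stops, followed to day 365 | no | no | **completer** |
| On, exits day 20 before stopping | no | no | **completer** |

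Bold marks a misclassification. The results are the same when the termination date is missing and the last visit date is used. Subjects with a recorded stop date come out as intended under both conventions.

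**Size.** Take N = 88 and no early exits, with a share *f* discharged off therapy and a share *g* of all 88 never stopping.

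- Intended count = N − gN
- Count under A = N − fN − gN, so too low by fN
- Count under B = N, so too high by gN

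Over the assumed range f = 10–70%:
- 0.10 × 88 = 8.8, about 9
- 0.70 × 88 = 61.6, about 62

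Over g = 0–20%:
- 0 × 88 = 0
- 0.20 × 88 = 17.6, about 18

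One point within the range: f = 30% (26 subjects) and g = 10% (9 subjects) give intended 79 (89.8%), A 53 (60.2%) and B 88 (100%).

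In the subgroup columns with no early exits, A shows 0% completers among those discharged off therapy, and B shows 100% among those discharged on it.

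**The case against.** The strongest reply is that little depends on this row. SAP 7.1 is the only place that uses the flag. It does not define the SAF, the per-protocol population, the primary endpoint derivation, the estimate with its 90% CI or any sensitivity analysis. That stands, and it limits the point to the disposition table. A reader might infer that the primary result is affected; the documents do not support that.

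A reader might also infer that the rule conceals how many subjects could not stop therapy. That goes too far. SAP 8.3 summarises ACT/DAPT status and its discontinuation by visit, SAP 8.5 tabulates concomitant medication, SAP 11.2 groups subjects by medication stopped at least 30 days before the first CT, and SAP 5.1 lists all data. An implausible 0% or 100% in an on/off column might also be noticed.

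Nor can one say that everyone discharged off therapy is misclassified under A. Those who leave before discharge + 31 days are correctly non-completers.

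The reference definition is itself unsettled. The gloss in SAP 5.4, "namely who discontinued the ACT/DAPT at minimum 30 days", read alone also overlooks subjects discharged off therapy, and the row encodes that gloss. For subjects discharged on therapy, SAP 5.4 ends the post-implant period at the discontinuation visit, whereas 18.13 ends it 30 days later; on the 5.4 period text alone, the fourth profile would be a completer. This stands as a reason to reconcile the texts together. It does not rescue the row, because completers are defined by a period that both sections branch by therapy at discharge.

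Finally, never-stoppers may be few, since Protocol 6.3.3 excludes subjects with a condition requiring long-term therapy. With none, and no early exits, convention B gives no error. Hence the range starts at zero.

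**Conclusion.** The point holds as a derivation error with limited reach. As written, the completer row cannot classify both groups lacking a stop date: A loses off-at-discharge subjects followed past discharge + 30 days, and B admits never-stoppers and early exits who have no stop date. The disposition count would be about 9–62 subjects too low or about 0–18 too high for 88 subjects without early exits. Those figures rest on assumed shares, as the documents give none. Early exits would add to the error under B and reduce it under A.

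The conclusion rests on ACTDIDAT being blank for both groups, which is likely but inferred. That B is what the program would produce rests on SAS behaviour. The either/or argument does not need it.

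**What to change.** Branch the completer row in SAP 18.13 on SCDISCYN:

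- **SCDISCYN = No:** hospital-discharge VISDAT not missing, and DSSTDAT (or last VISDAT if DSSTDAT is missing) ≥ that date + 31.
- **SCDISCYN = Yes:** discontinuation date not missing, and DSSTDAT (or last VISDAT) ≥ that date + 31.

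Use one anchor for the second branch, in both the completer row and the period rows. At present the completer row uses ACTDIDAT and the period rows use the VISDAT of the discontinuation visit. Protocol 7.5 allows that visit to be a planning visit, so the two dates can differ. If VISDAT is chosen, a recorded stop of therapy must remain a condition, or never-stoppers who attended the visit would count.

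In SAP 5.4, reword the completer gloss to cover subjects discharged off therapy, and reconcile the end of the post-implant period with 18.13. Add a disposition row in SAP 7.1 for subjects who never discontinued ACT/DAPT.

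The cost is a few lines of SAP text, matching program logic and one table row. SAP 18.13 already uses all the fields, so no new data are needed.
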